6.3.5. ACR50 and ACR70

ACR50 and ACR70 are similarly defined as ACR20 (see Section 6.3.4.), except the improvement threshold from core baseline is 50% and 70%, respectively

6.3.6. DAS28(CRP)

The DAS28(CRP) score is calculated as follows:

$$\text{DAS28(CRP)} = 0.56\sqrt{\text{TJC28}} + 0.28\sqrt{\text{SJC28}} + 0.36 \ln(\text{CRP} + 1) + 0.014 \times \text{SGA} + 0.96,$$

where

CRP = CRP measurement (mg/L)

SGA = subject's global assessment of disease activity on a 0-100 mm VAS

Higher DAS28(CRP) value indicates more severe disease activity.

No component-level imputation will be performed for the calculation of DAS28(CRP) for the primary analyses. If any components are missing, the DAS28(CRP) will be set as missing.

6.3.7. SDAI and CDAI

Simplified Disease Activity Index (SDAI) is a composite measure that sums the TJC28, SJC28, the SGA on a 0-10 cm scale, the PGA on a 0-10 cm scale, and the CRP (mg/dL). SDAI is scored as follow {Aletaha 2005}:

$$\text{SDAI} = \text{TJC28} + \text{SJC28} + \text{SGA} + \text{PGA} + \text{CRP}$$

Higher SDAI score indicates more severe disease activity status.

Clinical Disease Activity Index (CDAI) is a further simplification of the SDAI that excludes the CRP, which is calculated using the following formula {Aletaha 2005}:

$$\text{CDAI} = \text{TJC28} + \text{SJC28} + \text{SGA} + \text{PGA}$$

CDAI can range from 0 to 76, with higher score indicating more severe disease activity status.

No component-level imputation will be performed for the calculation of both SDAI and CDAI. If any components are missing, the SDAI and CDAI will be set as missing.

6.3.8. ACR-N

ACR-N is defined as the smallest percentage improvement from core baseline in swollen joints, tender joints and the median of the following 5 items (PGA, SGA, Patient pain assessment, HAQ-DI score and CRP). It has a range between 0 and 100%. In particular,

ACR-N = min {improvement in TJC68 (%), improvement in SJC66 (%), median [improvement in SGA (%), improvement in PGA (%), improvement in pain assessment (%), improvement in HAQ-DI (%), improvement in CRP (%)]}.

If this calculation results in a negative value, then the ACR-N is set to 0. If any components are missing, the ACR-N will be set as missing.

6.3.9. EULAR Response

Subject’s response will be categorized according to the following table based on the DAS28(CRP).

Table 6-2. EULAR Response Criteria

DAS28(CRP) at Visit	DAS28(CRP) Improvement from Core Baseline		
	> 1.2	> 0.6 and ≤ 1.2	≤ 0.6
≤ 3.2	Good Response	Moderate Response	No Response
> 3.2 and ≤ 5.1	Moderate Response	Moderate Response	No Response
> 5.1	Moderate Response	No Response	No Response

6.3.10. ACR/EULAR remission

ACR/EULAR remission is achieved when $TJC28 \leq 1$ and $SJC28 \leq 1$ and $CRP \leq 1$ mg/dL and $SGA \leq 1$ (on a 0-10 cm scale). ACR/EULAR remission is not achieved when at least 1 of the 4 components has a value > 1.

In case that some components are missing, ACR/EULAR remission is not achieved if at least 1 of the non-missing components has a value > 1. If non-missing components are not sufficient to determine ACR/EULAR remission, then ACR/EULAR remission will be considered as missing.

6.3.11. Health-Related Quality of Life (HRQoL)

HRQoL questionnaires consist of Short-Form 36 Health Survey (SF-36), and FACIT-Fatigue.

SF-36

The SF-36 is a 36-item, self-reported, generic, comprehensive, and health-related quality of life questionnaire that yields an 8 health domains (physical functioning, role-physical, bodily pain, general health, vitality, social functioning, role-emotional, and mental health). Each domain is scored by summing the individual items and transforming the scores into a 0 to 100 scale with higher scores indicating better health status or functioning. In addition, 2 summary scores, the physical component summary (PCS) score and the mental component summary (MCS) score will be evaluated based on the 8 SF-36 domains.

FACIT-Fatigue

The FACIT-Fatigue scale is a brief, 13-item, symptom-specific questionnaire that specifically assesses the self-reported severity of fatigue and its impact upon daily activities and functioning in the past 7 days. The FACIT-Fatigue uses 0 (“not at all”) to 4 (“very much”) numeric rating scales. Negatively stated items are reversed by subtracting the response from “4” before being added to obtain a total score. FACIT-Fatigue ranges from 0 to 52 with higher score indicating less fatigue. In the case of missing response for some items in the questionnaire, if at least half of the items (ie, ≥ 7 of 13 items) were answered at a given visit, the prorated score will be calculated and used in the analysis.

6.4. Analysis of the Efficacy Endpoint

For binary efficacy endpoints both OC and NRI data will be summarized using descriptive statistics (counts and proportions of subjects) by treatment and visit. For continuous efficacy endpoints, OC data will be summarized using descriptive statistics (sample size, mean, SD, median, Q1, Q3, minimum and maximum) by treatment and visit. No formal statistical testing is planned.

Plots of proportions of subjects for categorical endpoints and mean \pm SD for continuous endpoints will be presented over time by treatment and by visit.

6.5. Changes From Protocol-Specified Efficacy Analyses

There are no deviations from the protocol-specified efficacy analyses.

7. SAFETY ANALYSES

7.1. Adverse Events and Deaths

7.1.1. Adverse Event Dictionary

Clinical and laboratory adverse events (AEs) will be coded using the MedDRA Version 21.0. System organ class (SOC), high-level group term (HLGT), high-level term (HLT), preferred term (PT), and lower-level term (LLT) will be provided in the AE dataset.

7.1.2. Adverse Event Severity

Adverse events are graded by the investigator as Mild, Moderate and Severe according to toxicity criteria specified in the protocol. The severity grade of events for which the investigator did not record severity will be categorized as “missing” for tabular summaries and data listings. The missing category will be listed last in summary presentation.

7.1.3. Relationship of Adverse Events to Study Drug

Related AEs are those for which the investigator selected “Possible”, “Probable” or “Certain” on the AE CRF to the question of “Causality”. However, the investigator’s original answer to the question will be showed in the by-subject data listings. Relatedness will always default to the investigator’s choice, not that of the Medical Monitor. Events for which the investigator did not record causality will be considered related to study drug for summary purposes. However, by-subject data listings will show the relationship as missing.

7.1.4. Serious Adverse Events

Serious adverse events (SAEs) will be identified and captured as SAEs if AEs met the definitions of SAE that were specified in the study protocol. SAEs captured and stored in the clinical database will be reconciled with the SAE database from the Gilead Pharmacovigilance & Epidemiology (PVE) Department before data finalization.

7.1.5. Treatment-Emergent Adverse Events

7.1.5.1. Definition of Treatment-Emergent Adverse Events

Treatment-emergent adverse events (TEAEs) are defined as any AEs with an onset date on or after the filgotinib start date in the core studies or GLPG0634-CL-205, and no later than 30 days after permanent discontinuation of filgotinib in GLPG0634-CL-205.

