8.3.2 Inclusion Criteria

To be eligible for study entry subjects must fulfill all of the following criteria:

1. Male or female subjects who are ≥ 18 years of age, having completed one of the qualifying core studies GLPG0634-CL-203 or GLPG0634-CL-204 and, who in the opinion of the investigator, will continue to benefit from treatment in the extension study.
2. Female subjects of childbearing potential who engage in heterosexual intercourse must agree to use protocol specified method(s) of contraception and agree to refrain from egg donation and in vitro fertilization as described in Appendix 13.8.
3. Fertile male subjects who engage in heterosexual intercourse must agree to use protocol specified method(s) of contraception and agree to refrain from sperm donation as described in Appendix 13.8.
4. Able and willing to sign the informed consent as approved by the Independent Ethics Committee (IEC)/Institutional Review Board (IRB), prior to the Entry visit and agree to the schedule of assessments.

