8.3.3 Exclusion Criteria

Subjects will be excluded from the study if one or more of the following statements are applicable:

1. Subjects who had been prematurely withdrawn from one of the 2 core studies (GLPG0634-CL-203 or GLPG0634-CL-204), for any reason, including fulfilling the individual stopping criteria.
2. Subjects who are deemed not to be benefiting from the study medication based upon lack of improvement or worsening of their symptoms. Local guidelines for subject treatment need to be followed.
3. Subjects with persistent abnormal laboratory values, associated with the use of the study medication (including but not limited to hematology, liver and renal function values) during one of the 2 core studies (GLPG0634-CL-203 and GLPG0634-CL-204), according to the investigator's clinical judgment.
4. Subjects who require immunization with live/live attenuated vaccine.

5. Subjects with diagnosis since the inclusion to GLPG0634-CL-203 or GLPG0634-CL-204 core studies of rheumatic autoimmune disease or inflammatory joint disease other than RA, except for secondary Sjögren's syndrome.
6. Subjects with symptoms suggestive of moderate to severe congestive heart failure or major cerebrovascular event since the inclusion to GLPG0634-CL-203 and GLPG0634-CL-204 core studies.
7. Subjects with symptoms suggestive of GI tract ulceration and/or active diverticulitis since the inclusion to GLPG0634-CL-203 and GLPG0634-CL-204 core studies.
8. Subjects with symptoms suggestive of possible lymphoproliferative disease including lymphadenopathy or splenomegaly since the inclusion to GLPG0634-CL-203 and GLPG0634-CL-204 core studies.
9. Subjects with symptoms suggestive of malignancy since the inclusion to GLPG0634-CL-203 and GLPG0634-CL-204 core studies.
10. If applicable to national or local legislation: history of being admitted to an institution under administrative or court order since the inclusion to GLPG0634-CL-203 and GLPG0634-CL-204 core studies.
11. History of drug and alcohol abuse since the inclusion to GLPG0634-CL-203 and GLPG0634-CL-204 core studies.
12. Any condition or circumstances which, in the opinion of the investigator, may make a subject unlikely or unable to complete the study or comply with study procedures and requirements.

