3.1.2. Safety Analysis Set

The Safety Analysis Set includes all subjects who enrolled in GLPG0634-CL-205 and received at least one dose of study drug in GLPG0634-CL-205. This is the primary analysis set for safety analyses.

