3.2. Subject Grouping

For analyses based on the FAS subjects will be grouped according to the treatment to which they were randomized or assigned in GLPG0634-CL-205. For analyses based on the Safety Analysis Set, subjects will be grouped according to actual treatment received in GLPG0634-CL-205. The actual treatment received will differ from the randomized treatment only when their actual treatment differs from randomized treatment for the entire GLPG0634-CL-205 treatment duration.

Subjects will be presented by the following groups:

- Filgotinib with MTX
- Filgotinib monotherapy

The filgotinib with MTX group includes subjects who were from GLPG0634-CL-203 and randomized or assigned to filgotinib 100 mg q.d., filgotinib 100 mg b.i.d. or filgotinib 200 mg q.d. in GLPG0634-CL-205. The filgotinib monotherapy group includes subjects who were from GLPG0634-CL-204 and randomized or assigned to filgotinib 100 mg q.d., filgotinib 100 mg b.i.d. or filgotinib 200 mg q.d. in GLPG0634-CL-205.

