4.2. Extent of Filgotinib Exposure

Total duration of exposure to filgotinib will be defined as (last dose date of filgotinib in GLPG0634-CL-205 - first dose date of filgotinib in the core studies or GLPG0634-CL-205 + 1), regardless of any temporary interruptions in administration and will be expressed in weeks using up to 1 decimal place (eg, 4.5 weeks).

If the last filgotinib dosing date is missing, the latest date among the clinical visit date and laboratory sample collection date that occurred during the on-treatment period will be used.

If subjects are continuing on study drug, The data cutoff date will be used to impute the last dosing date for the calculation of the duration of exposure to filgotinib.

The total duration of exposure to filgotinib will be summarized using descriptive statistics and using the number (ie, cumulative counts) and percentage of subjects exposed for filgotinib baseline and every 12 weeks afterwards.

Summaries will be provided by treatment group for the Safety Analysis Set. No formal statistical testing is planned.

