7.1.6.1. Summaries of AE incidence in Combined Severity Grade Subsets

The number and percentage of subjects who experienced at least 1 TEAE will be provided and summarized by SOC, HLT, PT, and treatment group. For other AEs described below, summaries will be provided by SOC, PT, and treatment group:

- TEAEs of Grade severe
- TEAEs of Grade moderate or higher
- All TE treatment-related AEs
- TE Treatment-related AEs of Grade severe
- TE Treatment-related AEs of Grade moderate or higher
- All TE SAEs
- All TE treatment-related SAEs
- All TEAEs leading to premature discontinuation of any study drug
- All TEAEs leading to premature discontinuation of study
- All TEAEs leading to temporary interruption of any study drug
- All TE SAEs leading to death (ie, outcome of death)

A brief, high-level summary of AEs described above will be provided by treatment group and by the number and percentage of subjects who experienced the above AEs. All deaths reported in the study will be also included in this summary.

Multiple events will be counted only once per subject in each summary. Adverse events will be summarized and listed first in alphabetic order of SOC and HLT within each SOC (if applicable), and then by PT in descending order of total frequency within each SOC. For summaries by

severity grade, the most severe grade will be used for those AEs that occurred more than once in an individual subject during the study.

In addition to the above summary tables, all TEAEs and TE treatment-related AEs will be summarized by PT only, in descending order of total frequency.

In addition, data listings will be provided for the following:

- All AEs, indicating whether the event is treatment emergent
- All AEs of Grade severe
- All AEs of Grade moderate or higher
- SAEs
- Deaths
- All SAEs leading to death (ie, outcome of death)
- AEs leading to premature discontinuation of any study drug
- AEs leading to premature discontinuation of study
- AEs leading to temporary interruption of any study drug

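### The planned safety tables omit TEAEs leading to dose reduction, never isolate 200 mg/day, and show no general TEAE, SAE or infection results for study 205 alone

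*SAP*

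**What the plan says.** **Clock.** SAP 7.1.5.1 defines TEAEs as "any AEs with an onset date on or after the filgotinib start date in the core studies or GLPG0634-CL-205", up to 30 days after filgotinib is permanently stopped in GLPG0634-CL-205 (study 205). Exposure (SAP 4.2) is counted from the "first dose date of filgotinib in the core studies or GLPG0634-CL-205 + 1". For most subjects that date lies in a core study; for study 203 placebo responders it lies in 205.

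**Population.** "The Safety Analysis Set includes all subjects who enrolled in GLPG0634-CL-205 and received at least one dose of study drug in GLPG0634-CL-205" (SAP 3.1.2). Entry to 205 requires "having completed one of the qualifying core studies GLPG0634-CL-203 or GLPG0634-CL-204" (Protocol 8.3.2). Protocol 8.3.3 excludes "Subjects who had been prematurely withdrawn from one of the 2 core studies (GLPG0634-CL-203 or GLPG0634-CL-204), for any reason".

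**Tables.** "The number and percentage of subjects who experienced at least 1 TEAE will be provided and summarized by SOC, HLT, PT, and treatment group" (SAP 7.1.6.1). The tables by action taken cover premature discontinuation of drug, premature discontinuation of study, and "All TEAEs leading to temporary interruption of any study drug".

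**Columns.** SAP 3.2 presents two groups, filgotinib with MTX (from study 203) and monotherapy (from study 204). Each holds subjects "randomized or assigned to filgotinib 100 mg q.d., filgotinib 100 mg b.i.d. or filgotinib 200 mg q.d. in GLPG0634-CL-205". Actual treatment replaces assigned treatment only if it differed throughout 205.

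**Protocol.** The synopsis gives the primary endpoint as long-term safety and tolerability of 200 mg q.d. and 100 mg b.i.d. Section 8.9.1.3 commits to tabulating dose reductions, allows the three studies to be combined, and makes a patient-year analysis and a split by mean actual dose optional. SAP 7.7 reports no departure from the protocol's safety analyses.

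**The concern.** The study exists to describe the long-term safety of 200 mg/day. Three features of the tables stand in the way.

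- A tolerability outcome that the protocol promises, dose reduction, has no table.
- Neither displayed column corresponds to the dose in the primary endpoint. A subject reduced to 100 mg q.d. during 205 stays in the same column.
- The general TEAE tables mix events from up to 24 weeks of core filgotinib with events in 205. Everyone in the analysis set had, by the entry criteria, survived and completed that core period. It adds exposure time in which no member of the set could have died or withdrawn.

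At stake is whether a reader can say from the tables what happened in 205, and at which dose. Any later rate per patient-year also needs the right denominator.

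**Working it through.** **1. Dose reductions (comparison of text).** Protocol 8.9.1.3 lists dose reductions among the items to be tabulated. Protocol 8.8.1.2.1.1 makes dose reduction a recorded action category, so the data exist. SAP 7.1.6.1 has tables for discontinuation and interruption and none for reduction. SAP 7.7 states no deviation. These do not agree.

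**2. Dose pooling (comparison of text).** The endpoint names two 200 mg/day regimens, and each SAP 3.2 group adds 100 mg q.d. to them. SAP 1.2 says US males were limited to 100 mg q.d. Neither their number nor the number of dose-reduced subjects is given, so no size can be computed.

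**3. The plan's own figure.** 0.7 × (595 + 280) = 612.5, which agrees with the stated 612. Actual enrolment was 739 (Protocol 8.3.1), used below on the assumption that all were dosed.

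**4. Core time in the exposure summary.**
- Arm sizes (Protocol Tables 6-1 and 6-2): 594 + 283 = 877 subjects, of whom 508 + 211 = 719 were on filgotinib from the start.
- Filgotinib-exposed totals, back-solved from the percentages in Protocol 6.4: 538 (or 542) in 203 and 276 in 204. With 538, 814 were exposed, so 814 − 719 = 95 were placebo switchers.
- 24 weeks = 0.460 years, 12 weeks = 0.230 years; full core courses assumed.
- Core time: 719 × 0.460 + 95 × 0.230 = 352.6 PY.
- Carried into 205, with equal roll-over across arms: 352.6 × 739/877 = 297 PY.
- Lower bound, all switchers and all 63 never-exposed subjects roll over: 581 × 0.460 + 95 × 0.230 = 289 PY.
- Upper bound, all from-start subjects except 28 AE discontinuers (21 in 203, 7 in 204) roll over: 691 × 0.460 + 48 × 0.230 = 329 PY.

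**5. Effect on a death or withdrawal rate, if one were formed on this clock.** Shortfall = 297/(739m + 297), where m is mean years in 205. Attrition of 0-20% a year is assumed; the documents give none.

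| Time point | m at 0% | m at 20% | Shortfall |
|---|---|---|---|
| Week 156 | 2.99 | 2.18 | 11.8% to 15.6% |
| 96 months | 8 | 3.73 | 4.8% to 9.7% |

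**6. Ceilings on non-fatal rows, from core counts in Protocol 6.4.**
- Serious TEAE: 11 + 8 = 19 filgotinib subjects, of whom 11 to 13 stopped because of it. At most 8 are carried: 8/739 = 1.1 points.
- Herpes zoster: 4 + 1 = 5; 5/739 = 0.7 points.
- Serious infection: 5 + 4 = 9, less the 5 + 2 that led to discontinuation (read as permanent), leaves 2; 2/739 = 0.3 points.
- TB, opportunistic infection, malignancy: none reported in either core study, so 0.
- Venous thromboembolism, GI perforation, hepatitis B or C: the protocol gives no core counts, so no ceiling can be stated.

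**7. Net rise for common rows.** Rise = c × E[exp(−hT)]. Here c is the share with a core TEAE, h = −ln(1 − p)/0.460 is an assumed constant hazard, and T is follow-up in 205 under the same attrition range. Core and 205 events are taken as independent. The 28 AE discontinuers cannot be in the set, so they are removed from c: 877 − 28 = 849.
- Any TEAE: p = (277 + 114)/814 = 48.0%, h = 1.42 per year, c = (391 − 28)/849 = 42.8%. At Week 156, E runs from 0.014 to 0.142, so the rise is 0.6 to 6.1 points.
- Treatment-related TEAE: p = (109 + 46)/814 = 19.0%, h = 0.459 per year. If all 28 had related events, c = 127/849 = 15.0%. E runs from 0.253 to 0.414, so the rise is 3.8 to 6.2 points. If none of the 28 did, c = 155/849 = 18.3% and the upper end is 7.6.

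If TEAEs cluster in the same subjects, the rises are smaller.

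**The case against.** The pooled clock is permitted and declared: Protocol 8.9.1.3 allows the studies to be combined and SAP 1.1 says core data will be used. TEAEs, exposure, reference date and baseline share one origin, which makes a coherent all-filgotinib analysis. That stands, so pooling is not a deviation.

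A reader might infer that reported death or withdrawal rates will be 12-16% too low. The documents do not support that. The SAP plans counts and percentages, disposition percentages use the number of subjects (SAP 4.1), and the patient-year analysis is only an option.

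A reader might also infer that nothing planned shows 205 on its own. That goes too far. For core completers, deaths and study discontinuations can only have happened in 205, and both are tabulated. TB, opportunistic infection and malignancy rows are in effect 205 rows. Protocol 8.5.1 scopes MACE adjudication to events during the study. The AE listings are chronological within subject.

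Nor do the documents support a claim that lower-dose core events distort the profile. About 69% of core filgotinib time was below 200 mg/day, (480 × 0.460 + 95 × 0.230)/352.6, but Protocol 6.4 reports no clear dose relationship for treatment-related TEAEs.

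On dose, the primary objective names none, Protocol 8.6.1 lists 100 mg q.d. among the doses evaluated, and the dose split is optional. The endpoint nevertheless names the two 200 mg/day regimens, and no table shows them.

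Finally, the SAP was written against amendment 3 and the protocol supplied is amendment 4. The visible change log does not touch section 8.9.1.3, but amendment 3 itself was not available, so its wording at that time is inferred.

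**Conclusion.** The point holds as a reporting gap that should be fixed. It is not a bias in any planned estimate.

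- The missing dose-reduction table conflicts with the protocol as supplied and needs no assumption beyond the amendment caveat.
- No planned safety table isolates 200 mg/day. The size is unknown because the number on 100 mg q.d. is not given.
- No general TEAE, SAE or infection table shows 205-onset events alone. The carried core events can only raise non-fatal rows, which is the cautious direction: by at most about 1.1, 0.7 and 0.3 points for serious TEAEs, herpes zoster and serious infection. For any TEAE or treatment-related TEAE the rise is up to about 6 points at Week 156, given constant hazard, independence and 0-20% annual attrition. The treatment-related figure also takes the discontinuers' events as related.
- The 297 PY (289 to 329) of core time affects no planned ratio. It would matter only for a patient-year rate of death or withdrawal: about 12-16% too low at Week 156 and 5-10% at 96 months, at 297 PY and the same assumed attrition.

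**What to change.** 1. Add a table of TEAEs leading to dose reduction and correct SAP 7.7.
2. Add TEAE, SAE and AESI tables restricted to onset on or after the first 205 dose, with exposure counted from that dose.
3. Give these tables columns by assigned 205 regimen: 200 mg q.d., 100 mg b.i.d. and 100 mg q.d. Add the same columns to the death and disposition tables already planned; new count tables for those are not needed.
4. Where dated dose records allow, show dose at onset as a descriptive display.
5. Use 205 exposure for any patient-year rate of deaths or withdrawals. Count these by event date, not AE onset, because unresolved core AEs are carried onto the 205 pages (Protocol 8.7.1.1).
6. Keep the all-filgotinib tables, labelled as conditional on core completion.

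The cost is one more table set on data already held; SAP 3.5.1 already derives the first 205 dose date. Stated exposure falls by up to 24 weeks per subject, and first-exposure events appear only in the all-filgotinib tables. A carried AE that changes intensity in 205 is recorded as a separate event (Protocol 8.8.1.2.1.1) and stays in. Dose at onset costs more, since SAP 3.5.1 derives only first and last dose dates. Its 100 mg q.d. rows will include subjects reduced for intolerance or safety, so it cannot serve as a dose comparison.
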